8.6 Clinical Laboratory Evaluations

The following laboratory tests will be performed at Screening (Visit 1) and EOS (Visit 6):

- Clinical Chemistry: Alanine aminotransferase (ALT), Alkaline Phosphatase (ALP), Aspartate aminotransferase (AST), Bicarbonate (HCO₃), Bilirubin (Total, Direct, Indirect), Blood Urea Nitrogen (BUN), Calcium (Ca), Chloride (Cl), Creatinine, Glucose, Magnesium (Mg), Phosphorus (P), Potassium (K), Protein (Total), Sodium (Na), Uric Acid, Albumin

- Hematology: Hemoglobin, Hematocrit, Platelet Count, RBC Count, WBC - Total Count, WBC Differential, (Basophils, Eosinophils, Lymphocytes, Monocytes, Neutrophils)
- Urinalysis: Blood, Glucose, Ketones, Leukocyte esterase, Microscopic examination, Nitrites, pH, Protein

Summary statistics for these laboratory panels (clinical chemistry, hematology and urinalysis) will be provided by treatment group and visit. Laboratory data will also be summarized in shift tables presenting summary statistics of raw data and change from baseline values (means, standard deviations, medians, ranges). All clinical laboratory assessments will be listed for each panel.

In addition, the incidence of markedly abnormal post-baseline laboratory values (MAPLV) will be presented to examine the frequency and percentage of subjects that have values that are potentially clinically significant (PCS). These criteria are outlined in Appendix 14.4.

8.7 Physical and Neurological Examinations

A full physical examination will be performed at Screening (Visit 1) and at the EOS (Visit 6). Body weight will also be measured at Screening (Visit 1), Visit 4, Visit 5, and at the EOS (Visit 6). Height will be measured at Screening (Visit 1).

Clinically significant physical examination findings, as judged by the investigator, at screening will be recorded as medical history and after screening will be recorded as AEs or pre-treatment events depending on the timing in relationship to the first dose of study drug. Abnormal physical exam results will appear in medical history and/or AEs displays and will not be displayed separately.

Neurological examinations will be performed at Screening (Visit 1) and at the EOS (Visit 6) and the parameters will be assessed by the investigator as normal or abnormal. Neurological examination assessments will be summarized using summary statistics for categorical variables (normal/abnormal) by visit. A shift table for baseline condition versus the worst result during the course of the study period (Abnormal > Normal) will be presented by treatment.

8.8 Vital Signs

Vital signs, including respiratory rate; body temperature; supine, standing, and orthostatic blood pressure; supine, standing, and orthostatic heart rate; BMI; and body weight, will be measured at all scheduled in-person study visits (Screening [Visit 1 and Visit 2], Visit 4, Visit 5, and EOS [Visit 6]).

Supine systolic blood pressure, standing systolic blood pressure, orthostatic systolic blood pressure, supine diastolic blood pressure, standing diastolic blood pressure, orthostatic diastolic blood pressure, supine heart rate, standing heart rate, orthostatic heart rate, respiratory rate, body temperature, body weight, and BMI will be summarized descriptively for each visit by treatment group for the absolute value and change from baseline values using descriptive statistics.

In addition, the incidence of sponsor-defined markedly abnormal post-baseline vital sign values will be presented to examine the frequency and percentage of subjects that meet the PCS criteria outlined in Appendix 14.5.

8.9 Electrocardiography (ECG)

A 12-lead ECG will be recorded at Screening (Visit 1) and the EOS visit (Visit 6). All ECGs will be obtained in the supine position, after the subject has been resting supine for at least 5 minutes. The ECG parameters collected will include heart rate, PR interval, RR interval, QT interval, QTc with Bazett correction (QTcB) and QTc with Fridericia correction (QTcF) intervals, QRS duration, and interpretation, including any noted abnormalities. The ECGs will be reviewed and interpreted by the investigator. All data will be assessed for clinical significance.

ECG measurements, overall interpretation, and clinical significance will be summarized descriptively for baseline, each post-dose evaluation, and change from baseline to each post-dose evaluation by treatment group. QT interval, QTcB, and QTcF will also be summarized by < 460 msec, \geq 460 msec, < 500 msec, and \geq 500 msec, as well as change from baseline < 30 msec, \geq 30 msec, < 60 msec, and \geq 60 msec, by visit, treatment and age group (6-9 years, 10-13 years).

In addition, the incidence of sponsor-defined markedly abnormal post-baseline ECG values will be presented to examine the frequency and percentage of subjects that meet the PCS criteria outlined in Appendix 14.6.

8.10 Columbia Suicide Severity Rating Scale (C-SSRS)

The C-SSRS is a brief investigator-administered questionnaire that provides for the identification, quantification, and standardized assessment of the occurrences and severity of suicidal ideation and behavior. Subjects will be assessed at Screening (Visit 1) using the Children's Baseline/Screening C-SSRS. For all subsequent testing (Visits 2, 4 and 5 and the EOS visit), the Children's Since Last Visit assessment will be utilized.

The frequency of suicidality using the C-SSRS will be summarized for each visit for each of the following outcomes:

- Number of subjects reporting at least one occurrence of suicidal ideation or behavior.
- Number of subjects reporting any type of suicidal behavior.
- Number of subjects reporting any type of suicidal ideation.

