Multiplicity Considerations: There will be no adjustment for multiplicity for the primary efficacy analysis, secondary efficacy analyses, or safety analyses.

Safety Analysis:

All safety analyses will be performed on the safety population, which includes subjects that had been treated with dasotraline 6 mg/day. Overall AEs (or SAEs) and AEs (or SAEs) leading to discontinuation will be summarized by system organ class and preferred term by presenting the number and percentage

of subjects with each AE. Descriptive statistics also will be provided by visit for observed values and changes from baseline of the following safety variables: laboratory tests, vital signs, and ECG parameters. Frequency and severity of suicidality using the C-SSRS will be summarized by visit.

Sample Size: A post-baseline least square mean of 18.66 in mean SKAMP-Combined score obtained from an average of 7 assessments collected across the 12-hour classroom day was observed for the placebo group in a similarly designed study ([Wigal-2013](#)). It is assumed that the dasotraline group will have approximately 20% improvement in mean SKAMP-Combined score for dasotraline 4 mg/day versus placebo. The treatment mean difference in change from baseline is therefore assumed to be 4.0 units (effect size of 0.8) versus placebo on mean SKAMP-Combined score with a common standard deviation of 5 units for dasotraline 4 mg/day. The two-sample t-test with equal variance procedure using nQuery Version 7.0 was utilized for the sample size/power calculation. A total of 100 subjects (50 each for the dasotraline 4 mg/day and placebo groups) will provide at least 95% power to detect a statistically significant treatment difference for the dasotraline dose group versus placebo in the primary endpoint at a 5% significance level (2-sided).

The study will target approximately 110 subjects randomized to either placebo or dasotraline 4 mg/day in an attempt to have 100 subjects complete the trial. In addition, approximately another 20 subjects were randomized to dasotraline 6 mg/day under previous versions of the protocol. The total number of subjects randomized in this study will be approximately 130.

Table 2: Schedule of Assessments

| Procedures | Screening | | | Double-blind Period | | End of Study |
|---|---------------|---------------------------------------|-------------------|--------------------------------|---------------------------------|---------------------------|

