6.2. Secondary Endpoints

The secondary endpoints are:

- Mean SKAMP-Combined score from the 7 assessments collected across the 12-hour classroom day (12 to 24 hours postdose) on Day 15
- SKAMP-Combined score at each of the assessment times (12-, 14-, 16-, 18-, 20-, 22-, and 24-hours postdose) during the classroom day on Day 15
- Change from baseline at Day 15 in SKAMP-Combined score at each of the assessment times (12-, 14-, 16-, 18-, 20-, 22-, and 24-hours postdose) during the classroom day
- Change from baseline at Day 15 in mean SKAMP-Attention subscale score obtained from the 7 assessments collected across the 12-hour classroom day (12 to 24 hours postdose)
- SKAMP-Attention subscale score at each of the assessment times (12-, 14-, 16-, 18-, 20-, 22-, and 24-hours postdose) during the classroom day on Day 15
- Change from baseline at Day 15 in SKAMP-Attention subscale score at each of the assessment times (12-, 14-, 16-, 18-, 20-, 22-, and 24-hours postdose) during the classroom day
- Change from baseline at Day 15 in mean SKAMP-Deportment subscale score obtained from the 7 assessments collected across the 12-hour classroom day (12 to 24 hours postdose)
- SKAMP-Deportment subscale score at each of the assessment times (12-, 14-, 16-, 18-, 20-, 22-, and 24-hours postdose) during the classroom day on Day 15
- Change from baseline at Day 15 in SKAMP-Deportment subscale score at each of the assessment times (12-, 14-, 16-, 18-, 20-, 22-, and 24-hours postdose) during the classroom day
- Change from baseline at Day 15 in Permanent Product Measure of Performance (PERMP)-Attempted and Correct Problems scores at each of the assessment times (12-, 14-, 16-, 18-, 20-, 22-, and 24-hours postdose) during the classroom day
- PERMP-Attempted and Correct Problems scores at each of the assessment times (12-, 14-, 16-, 18-, 20-, 22-, and 24-hours postdose) during the classroom day on Day 15

- The incidence of overall AEs, serious AEs (SAEs), and AEs (or SAEs) leading to discontinuations
- Absolute values and change from baseline in clinical laboratory evaluations (serum chemistry, hematology, and urinalysis)
- Absolute values and changes from baseline in vital signs, body weights, and 12-lead ECGs
- Frequency and severity of suicidal ideation and suicidal behavior as assessed by the C-SSRS

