8. Subject has a history or presence of abnormal ECGs, which in the investigator's opinion is clinically significant. Screening site ECGs will be centrally over-read, and eligibility will be determined by the investigator based on the results of the over-read report.
9. Subject has any diagnosis of bipolar I or II disorder, major depressive disorder, conduct disorder, obsessive-compulsive disorder, any history of psychosis, autism spectrum disorder, disruptive mood dysregulation disorder (DMDD), intellectual disability, Tourette's Syndrome, confirmed genetic disorder with cognitive and/or behavioral disturbances. Note: Subjects with oppositional defiant disorder (ODD) are permitted to enroll in the study as long as ODD is not the primary focus of treatment.
10. Subject has generalized anxiety disorder or panic disorder that has been the primary focus of treatment at any time during the 12 months prior to screening or that has required pharmacotherapy any time during the 6 months prior to screening.
11. Subject has evidence of any chronic disease of the central nervous system (CNS) such as tumors, inflammation, seizure disorder, vascular disorder, potential CNS related disorders that might occur in childhood (eg, Duchenne Muscular dystrophy, myasthenia gravis, or other neurologic or serious neuromuscular disorders), or history of persistent neurological symptoms attributable to serious head injury. Past history of febrile seizure, drug-induced seizure, or alcohol withdrawal seizure is exclusionary. Subject taking anticonvulsants for seizure control currently or within the past 2 years is not eligible for study participation.
12. Subject has uncontrolled thyroid disorder as evidenced by thyroid stimulating hormone (TSH) $\leq 0.8 \times$ the lower limit of normal (LLN) or $\geq 1.25 \times$ the upper limit of normal (ULN) for the reference laboratory
13. Subject answers "yes" to "Suicidal Ideation" item 4 (active suicidal ideation with some intent to act, without specific plan) or item 5 (active suicidal ideation with specific plan and intent) for any lifetime history on the C-SSRS Children's Lifetime/Recent assessment at screening.
14. Subject has any history of attempted suicide or clinically significant suicidal ideation, in the opinion of the investigator.

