15.3.6.7. Columbia-Suicide Severity Rating Scale (C-SSRS)

The number of subjects having any suicidal behavior or suicidal ideation from the C-SSRS evaluation will be summarized.

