12.2 Changes in the Analysis Planned in the Protocol

No changes are planned as of the date of the SAP.

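### The protocol makes severity part of the C-SSRS secondary endpoint, but protocol 15.3.6.7 and SAP 8.10 specify only any/none counts, so no planned by-arm C-SSRS summary separates item 4 or 5 ideation from milder ideation

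*SAP*

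**What the plan says.** The protocol is not consistent with itself on this endpoint, and the SAP follows the narrower of its two versions.

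- Protocol 6.2, repeated in the synopsis endpoint list: "Frequency and severity of suicidal ideation and suicidal behavior as assessed by the C-SSRS".
- Protocol synopsis, safety analysis: "Frequency and severity of suicidality using the C-SSRS will be summarized by visit".
- Protocol 15.3.6.7: "The number of subjects having any suicidal behavior or suicidal ideation from the C-SSRS evaluation will be summarized". Severity is not mentioned.
- SAP 8.10 describes the C-SSRS as an instrument that captures both occurrence and severity, then states: "The frequency of suicidality using the C-SSRS will be summarized for each visit for each of the following outcomes". Three outcomes follow: "Number of subjects reporting at least one occurrence of suicidal ideation or behavior"; "Number of subjects reporting any type of suicidal behavior"; and the matching count for any type of ideation.
- SAP 12.2, on departures from the protocol's analyses: "No changes are planned as of the date of the SAP".

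The protocol does distinguish levels of ideation elsewhere. Exclusion 13 in section 8.2 bars a child who reports at screening item 4 (some intent to act, no specific plan) or "item 5 (active suicidal ideation with specific plan and intent) for any lifetime history".

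**The concern.** Part of a named secondary safety endpoint has no specified summary. The documents treat ideation with intent or a plan as important enough to bar entry. After dosing, the same levels fall into one count with any lesser ideation. The behavior count likewise merges all types of behavior.

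At stake is the comparison between arms. Two arms could have equal numbers of children with any ideation but differ in how severe it was, and the planned C-SSRS summaries would show no difference. These are children aged 6 to 12 on a centrally acting drug. Other safety domains in the SAP are summarized in more detail: laboratory values and the neurological examination get shift tables, vital signs get change from baseline and markedly-abnormal criteria, and QT intervals get threshold categories.

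**Working it through.** The plan states no figure here, so the check is a comparison of texts plus one logic test.

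**Step 1: what is promised and what is specified.** The synopsis and protocol 6.2 promise frequency and severity, and the synopsis adds by visit. Protocol 15.3.6.7 specifies an any/none count. SAP 8.10 specifies three any/none counts by visit. Severity is in the first pair and absent from the second.

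**Step 2: whether another SAP provision fills the gap.**
- SAP section 3 says categorical assessments are summarized by treatment group and time point with counts and percentages. It also says that a specific section prevails where it departs from the general policy. Section 8.10 names its own outcomes, so the general rule does not clearly add an item-level table.
- SAP section 3 says all study data are listed by subject, treatment group and time point. Item responses should therefore be visible case by case, but a listing is not the by-visit summary that the synopsis describes.
- SAP 8.5 (adverse events of special concern) contains no suicidality terms, so neither that summary nor the analyses in SAP section 10 that use it cover this.
- SAP 8.4 tabulates adverse events by maximum severity, seriousness and discontinuation. Suicidality recorded as an adverse event would appear there. However, mild, moderate and severe are a different scale from the C-SSRS items, and no text makes every positive C-SSRS response an adverse event.

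**Step 3: logic test.** The counts are assumed for illustration; the documents give no event rate. The arm size of 55 is the planned number for placebo and for 4 mg/day. Arm A has 3 children whose only ideation is item 1, arm B has 3 children at item 5, and neither arm has any behavior.

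| Outcome | Arm A | Arm B |
|---|---|---|
| Ideation or behavior (SAP) | 3 + 0 = 3 of 55 | 3 + 0 = 3 of 55 |
| Behavior (SAP) | 0 of 55 | 0 of 55 |
| Ideation (SAP) | 3 of 55 | 3 of 55 |
| Most severe item is 4 or 5 (not planned) | 0 of 55 | 3 of 55 |

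The three planned outcomes are identical, and only the last row separates the arms.

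**Step 4: whether the data exist.** The protocol's schedule of assessments has the C-SSRS at screening, Day -7, Day 1, Day 15 and end of study. The first dose is on the evening of Day 1, so Day 15 and end of study are the scheduled post-dose assessments. No new collection is needed.

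**The case against.** The strongest reply is that this is a wording mismatch with little consequence. SAP 8.10 agrees with the protocol's own statistics section and goes beyond it, with a breakdown and by-visit reporting. It does not say that its list is exhaustive. SAP section 1 places table and listing specifications in separate documents, which cannot be seen here. Listings would expose any item 4 or 5 response by arm and visit, and protocol 11.4.7 sends significant ideation to the investigator. Treatment lasts 14 days, arms are small, and children with relevant history are excluded, so events may be few.

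Much of this stands. The conflict does begin inside the protocol, so the SAP 12.2 statement is only weak evidence of an undeclared change. The data are not lost. But none of it supplies the promised severity summary, and unseen table specifications cannot stand in for the SAP.

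Three stronger readings are tempting, and the documents do not support them.

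- A reader might infer that every post-dose item 4 or 5 report must be a new escalation, because such children are excluded. Exclusion 13 applies to the screening assessment, which may be as early as Day -35. The C-SSRS is repeated before dosing on Day -7 and Day 1, so such ideation could first appear in that window. Exclusion 14 makes enrolment of such a child unlikely, but it rests on investigator opinion.
- A reader might infer that no such case could be identified. The listings, and possibly the adverse event tables, would show it.
- A reader might infer that half of the endpoint goes unreported. The documents give no basis for that fraction.

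**Conclusion.** The point holds as a gap between endpoint and analysis. The synopsis and protocol 6.2 promise severity; protocol 15.3.6.7 and SAP 8.10 do not specify it; and the SAP's general conventions do not clearly restore it. The consequence is that the plan contains no C-SSRS summary by treatment group that separates item 4 or 5 ideation from milder ideation, or one type of behavior from another.

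The size cannot be given as a number, because the documents state no expected event rate. The effect is confined to one secondary safety endpoint; the primary efficacy analysis is untouched. The conclusion assumes that SAP 8.10 is read as naming the complete set of C-SSRS summaries, which is the natural reading under the SAP's precedence rule but is not stated outright. It should be corrected before database lock.

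**What to change.** Reconcile the synopsis, protocol 6.2, protocol 15.3.6.7 and SAP 8.10. In 15.3.6.7 and SAP 8.10, keep the three existing counts and add, by treatment group and visit:

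- the number of subjects by most severe ideation item, including the number with item 4 or 5 after first dose;
- the number of subjects by type of suicidal behavior.

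A shift table from the worst pre-dose level (screening, Day -7 and Day 1) to the worst post-dose level is a cheap optional addition. It would distinguish new from pre-existing ideation, but the protocol does not promise it.

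If the sponsor prefers to report any/none counts only, SAP 12.2 should declare and justify that change.

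The cost is SAP and protocol wording plus one or two small tables, probably sparse, from data already collected. No assessment or procedure changes.

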9. PHARMACOKINETIC EVALUATION

No pharmacokinetic sampling is planned for this study.

10. OTHER ANALYSES

Data collected for the 6 mg/day dasotraline arm will be used for exploratory analyses. All subjects in the 6 mg/day arm will be analyzed using the same primary and secondary efficacy analysis methods described in Section 7.5 in a separate model from the 4 mg/day arm. They will also be analyzed for safety as described in Section 8, both separately and pooled with the 4 mg/day dasotraline group.

Dose response and tolerability for dasotraline treated subjects will also be analyzed in a weight-based dose-level analysis. Dose per weight (mg/kg) will be calculated for each dasotraline treated subject and then placed into the following groupings:

- 2 equal-sized groups: 2 groups will be formed based on the median number of dasotraline treated subjects. Each group will contain half of the population of dasotraline treated subjects.
- 3 equal-sized groups: 3 groups will be formed based on tertiles of the number of dasotraline treated subjects. Each group will contain a third of the population of dasotraline treated subjects.
- 4 equal-sized groups: 4 groups will be formed based on quartiles of the number of dasotraline treated subjects. Each group will contain a fourth of the population of dasotraline treated subjects.
- 2 equal-ranged groups: 2 groups will be formed based on the ranges of dose per weight (mg/kg) with cutoff points obtained at 2 equally spaced intervals over the range of mg/kg.
- 3 equal-ranged groups: 3 groups will be formed based on the ranges of dose per weight (mg/kg) with cutoff points obtained at 3 equally spaced intervals over the range of mg/kg.
- 4 equal-ranged groups: 4 groups will be formed based on the ranges of dose per weight (mg/kg) with cutoff points obtained at 4 equally spaced intervals over the range of mg/kg.

Each of these groupings will be analyzed using the same primary efficacy analysis method described in Section 7.5.1. In addition, each of these groupings will be analyzed for safety summarized by PT in descending order for each of the following categories: AEs, SAEs, AEs leading to discontinuation, and AEs of special concern.

A Receiver Operating Characteristic (ROC) analysis will also be conducted based on a logistic regression with dose per weight (mg/kg) as the predictor and AE of special concern as the outcome. An ROC curve for the model will be plotted. The predicted probability of having an AE of special concern event will also be plotted as a function of dose per weight (mg/kg).

Any additional analyses performed after finalization of the SAP will be considered exploratory and will be identified as such in the CSR.

